3.3 Randomization of schools to implementation interviews

Of the 20 original public schools selected to participate – 18 school principals agreed to participate and two declined Overbrook Elementary and McMichael Elementary are both ineligible to participate in staff surveys. In addition, 3 charter schools were selected for convenience for preliminary work and test.

Across the remaining schools, the goal was to select 2 more charter schools and 18 conventional public schools. To this end, we first assigned a random uniform (0,1) number to each school. Next, we ranked these random numbers within the charter schools and within the public schools. Third, we selected the 2 (charter) and the 18 schools (public) with the highest ranks (lowest rank numbers) for inclusion in the sample. This process was done by one of the statisticians, using a preselected seed for the random number generator and with no contact with any of the schools nor any information about the schools other than their names.

3.4 Allocation Concealment

For the individual child level randomization, all randomization lists were generated by one of the statisticians and then delivered to the REDCap database designers. Upon each child recruitment, REDCap then produced the treatment assignment for the next child and for the school of the child's attendance. All patients had to consent to the study (and sign consent forms) before the research coordinator could elicit from REDCap the treatment assignment for that child. By this method no one on the staff other than the database manager was aware of the next treatment assignment for the next child in the stratum of school*clinic.

4 Data Collection and Management

Data will be collected, accessed, and stored by the CHWs and study research team. Any paper forms will be stored in locked cabinets in the Community Asthma Prevention Program's (CAPP) badge-only accessible suite. Data collected using REDCap is accessible only by the CHWs and research study staff. Designated school administrators (i.e., principal), the school nurse and the child's primary care provider will only have access to participant health care information necessary to conduct asthma management in the schools and primary care office, but none of the research data collected by the CHWs and study staff. Information will be kept confidential under HIPPA guidelines and Institutional policies. Analysis will proceed on CHOP computers, either secure desktop machines or the CHOP virtual computing system based on VMWare, and all data will be stored on a CHOP server in directories created for this project. Access to each dataset with identifiers will be limited to the minimum necessary to accomplish the analytic tasks.

5 Analysis – Primary

5.1 Specific Aim 1. Compare the effectiveness of all combinations of clinic and schoolbased interventions to improve asthma control and reduce symptom days. We have selected a factorial design because of its enhanced statistical power and its ability to estimate contrasts of interest, even within the framework of a cluster randomized design. Chakraborty (2009). Collins (2014). The added complexity of a conventional within-school randomization (child-level intervention) crossed with cluster-randomization (school-level intervention) can be handled with the proposed model alternatives, each with a different set of assumptions, to demonstrate the robustness of the findings to model specification. (Peters 2003). Our statistical methods will also estimate variation across schools in the effect over time. (Fitzmaurice, Laird, & Ware, 2011; Gelman & Hill 2007; Hayes & Moulton, 2017).

We propose and pre-specify three alternative approaches, each of which has been used in conventional cluster randomized design. Each approach has assumptions, strengths, and weaknesses. We intend to report the results of all three approaches, provided that models will converge to results, in order to assess robustness of findings to model choice. We do not consider use of the three approaches to be multiple comparisons. Rather, we consider the use of multiple approaches to assess this additional component of variability.

5.1.1 Outcomes

Outcome and their priority appear in Table 5.1.1

Table 5.1.1

Study Outcome-Listed	Measurement	3	6	9	12
in Order of Priority	times				
	(month) 0				
Asthma	Х	Х	Х	Х	Х
(Asthma control					
questionnaire)					
PRIMARY					
Asthma quality of life	Х				Х
Number of	Х				Х
hospitalizations					
Number of emergency	Х				Х
department visits					
On or off controller	Х				Х
medication					
Courses of oral steroids	Х				Х
Number of school	Х				Х
absences					
ICD-10 J45.XX	Х				Х
Diagnosis-based					
encounters- to define					
relevant office,					
hospitalization, ED					
visits					

School absences. Each child will have two semesters (one years) before and after the start of the intervention from which to calculate absences. Absenteeism data will ideally come from the

schools. If schools are unable to provide absenteeism data, self-reported data will be utilized. We propose to evaluate the reliability and completeness of school absences data before, and independently from, formal analysis of the association of this and other outcomes and treatment assignment.

5.1.2 Measuring outcomes over time - irregular measurement times

Longitudinal model

Although the protocol calls for regular measurement times (Juniper's **Asthma Control Questionnaire** is a validated survey and will be administered by the CHW at baseline, 3 months, 6 months, 9 months and 12 months), in all likelihood these measurements will have the following characteristics. (1) They will not be administered at 3,6, 9 and 12 months. For some the schedule will lag. (2) Some children will miss one or more of these measurements.

Although some RCTs assume that measurements occur at the protocol-defined time, even when they do not, there is no reason for, and we shall deliberately avoid, that ad hoc practice.

We shall model the time of each measurement as the number of months (including factional amounts) from date of randomization. Time we shall model flexibly with splines. [Here we can use cubic splines as needed).

Choices for knots. We shall assume knots at time 3, 6 and 9 months, the intended dates of measurements.

With time measured flexibly, and with a statistical model that includes time by treatment (4 level) interactions, the spline model will allow for estimate of differences (or ratios) of outcomes at any point along the time (x) axis by treatment group.

Covariates -- selection and balancing

In theory randomization at the child level should balance on observed and unobserved factors. With children spread over 36 schools, and with chance differences across school, imbalances in child characteristics are possible at the school level but are not likely at the treatment assignment level (the four cells a, b, c and d). In addition, dropout can undermine the balance achieved in theory and in practice by randomization.

Key child-level covariates appear in Table 5.1.2.

Table 5.1.2 Covariates – baseline descriptions

Child level factors	Units of measurement or categories
AGE	Subgroups: 5-11; 12-13
GENDER	Male Female
Body mass index (weight in kg) (height in cm)	Collected and/or calculated by age-sex standardized percentile and/or z score. Both percentile and z will be used
HOUSEHOLD CHARACTERISTICS (descriptive only)	 (1) Single Parent/Caregiver vs Multiple Caregivers (2) Number of Adults in household (3) Number of Children in Household
Home environment	Number of bedrooms
Smoking	Smokers or none in home
Caregiver Education Highest level achieved by primary caregiver	Less than HS HS+ Graduate Level
Baseline Healthcare utilization	
Oral Steroid courses in the last year	None 1 course 2 courses 3 5 courses
ED With include - But describe in categories	>5 courses
ED VISITS in the last year	0, 1, 2, 3+
Continuous – Describe in categories Inpatient visits in the last year Continuous—Describe in categories	0,1,2, 3+

Data on height and weight, and BMI, and BMIz, will be downloaded from EPIC. BMI categories of interest are <85th percentile, 85th to 95th percentile, and 95% percentile or greater. Height is not done at each encounter. For that reason, height must be carried forward from the last available measurement time. This practice, though common, can result in a bias toward higher than actual BMI over time. Adjustments (e.g., interpolation) of height for measurement times between height measures is possible. If any interpolation of height, we shall do so without regard to measures of outcome.

For that reason, we shall first examine balance across the 4 treatment groups in child-level characteristics. To that end, we shall use conventional balancing diagnostics, such as comparison of percentages of patients by categorical factors and by standardized differences for continuous

factors, and/or comparisons of distributions. All will be supplemented by graphical display. These diagnostics are programmed and explained in the R program "cobalt" (Greifer 2019).

Treatment assignment model

Covariates that do not demonstrate balance will be included in an initial multinomial logit model (with the 4 treatments as outcomes). Then using generalized propensity scores, we will develop inverse probability of treatment assignment weights. This approach will then result in estimates of average treatment effects in the response model.

Response model—to estimate expected values over time

The response model will be a weighted longitudinal model using splines for time and time by treatment interaction terms. This model will result in the estimation of expected values at any given time post randomization for any of the four treatment categories.

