### 5 STUDY EVALUATIONS AND MEASUREMENTS

### 5.1 Individual Participant Measures

- Children will be measured for **height and weight** (using standard scales and stadiometers), **blood pressure**, **pulse**, **temperature**, and **pulse oximetry** (SpO2) at baseline, 3, 6, 9, and 12 months following enrollment. This information may also be abstracted from the medical record.
- Pulmonary function tests (spirometry) will be abstracted from the electronic health record if possible. If spirometry is not completed by the child's healthcare team as a part of usual clinical care, it will be completed by a trained community health worker at baseline, 3, 6, 9 and 12 months post-enrollment. Each recording will be printed out to become a part of the child's medical record. Pulmonary function testing completed for clinical purposes within one month before or after a baseline or

- follow-up study visit will be abstracted from the medical record if testing is unable to be completed at the time of a study visit.
- Juniper's **Asthma Control Questionnaire** is a validated survey and will be administered by a member of the research team to the parent/caregiver by reading out loud to avoid any literacy barriers. This will be administered at baseline, 3 months, 6 months, 9 months and 12 months
- A home **environmental assessment** will be conducted by a CHW in the living room and child sleeping area to note common triggers such as dust, pests, pets, mold and tobacco smoke measured at Home Visits 1, 2, 3, and 4.
- CAPP's **asthma knowledge survey** will be used to assess knowledge at home visits before, during and after the primary care intervention. This survey may be administered out loud to the parent/caregiver to avoid any literacy barriers.
- CHW will ask parent/caregiver for a 2-week recall of daytime cough or wheeze, nighttime cough or wheeze, missed school days, missed parent workdays at the time of the visit. This will be recorded on a tracking form in REDCap.
- The Caregiver Needs Assessment will be administered to the parent/caregiver at the baseline visit. The needs assessment is a validated instrument that focuses on the caregiver's knowledge about asthma avoidance measures and their comfort level with managing their child's asthma. For participants receiving the primary care intervention, this tool will assist the primary care community health worker with tailoring the educational component of the program to fit the needs of the individual family.

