### 5.3.3 Vital Signs

Weight will be measured with a standardized scale.

Height will be measured with a standardized stadiometer.

Blood pressure, pulse, temperature and SpO2 will be measured by clinic staff using standard clinical procedures and equipment. This information will be abstracted from the medical record by study staff.

Pulmonary function will be measured using a Morgan Scientific spirometer.

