### 6.3.3 Subgroup Analysis: Mediator and Moderator Variables

Baseline variables including asthma control, BMI, school type (public/charter) and demographic characteristics which may serve as moderators of intervention effectiveness will be evaluated through subgroup analyses. These variables will be used to identify subgroups of children that may be more likely to benefit from the study interventions. Mediator variables such as communication between school and primary care and level of participation in school-based asthma therapy will be evaluated to better understand the mechanism of effect of the intervention on the study's primary outcomes.

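### Baseline BMI may rest on an out-of-date chart height: the SAP carries height forward with no age limit and gives no priority to the height scheduled at Visit 1

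*SAP*

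**What the plan says.** The BMI rule is in SAP 5.1.2 (the section on irregular measurement times), next to Table 5.1.2:

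- Source: "Data on height and weight, and BMI, and BMIz, will be downloaded from EPIC".
- Gaps in height: "For that reason, height must be carried forward from the last available measurement time". No maximum age is given for the carried height.
- Known drawback: "This practice, though common, can result in a bias toward higher than actual BMI over time".
- Possible remedy: "Adjustments (e.g., interpolation) of height for measurement times between height measures is possible". The SAP adds that any interpolation would ignore the outcomes, but it does not commit to doing it.
- Use: "BMI categories of interest are <85th percentile, 85th to 95th percentile, and 95% percentile or greater". Percentile and z-score are both to be used.

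The protocol plans direct measurement. Section 5.1 has height and weight taken with scales and stadiometers "at baseline, 3, 6, 9, and 12 months following enrollment". Section 5.3.3 says: "Height will be measured with a standardized stadiometer". Sections 4.2.1 to 4.2.3 list weight, height and BMI for all participants at Visits 1 to 5.

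The protocol also leaves room for gaps. Sections 5.1 and 5.3.1 allow these values to come from the medical record. Section 3.1.3 lets control-arm data at 3, 6 and 9 months be collected by phone, and lets study visits be remote during the pandemic.

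BMI is used as a baseline variable. It is a key child-level covariate in SAP Table 5.1.2, and Protocol 6.3.3 names it as a possible moderator: "Baseline variables including asthma control, BMI, school type (public/charter) and demographic characteristics".

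**The concern.** The SAP argues that because routine encounters do not always include a height, height has to be carried forward. That does not follow for a trial that schedules its own height measurement at every data-collection visit. The SAP never says that a same-date study height takes precedence over an older chart height, and the only option it words as a requirement is the one it describes as prone to bias.

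Children aged 5 to 13 are growing. Dividing a current weight by the square of an older, smaller height overstates BMI, and with it the z-score and percentile. The error goes in one direction only.

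Two uses are exposed. First, BMI is checked for balance across the four treatment groups; if it is out of balance it enters the multinomial treatment model, whose weights feed the response model. Second, the protocol would use baseline BMI to look for subgroups that benefit more. Upward misclassification blurs the three BMI groups in both uses.

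**Working it through.** The documents give no figure that depends on height or BMI, so there is nothing of the plan's own to reproduce. The check concerns the size of the error if a carried height is *m* months old.

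**Step 1: overstatement of BMI.** BMI is weight divided by height squared. With current height *H* (cm), growth *g* (cm/year) and a height *m* months old:

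overstatement = (H / (H − g·m/12))² − 1

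Neither *H* nor *g* is in the documents. Assuming H = 128 and g = 6:

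| Age of height | Calculation | Overstatement |
|---|---|---|
| same day | (128/128)² − 1 | 0% |
| 3 months | (128/126.5)² − 1 | 2.4% |
| 6 months | (128/125)² − 1 | 4.9% |
| 12 months | (128/122)² − 1 | 10.1% |

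Over heights of 110 to 155 cm and growth of 4.5 to 7 cm/year, the ranges are 1.5–3.3% at 3 months, 3.0–6.7% at 6 months and 6.1–14.1% at 12 months.

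**Step 2: effect on the BMI categories.** Take BMI as lognormal with coefficient of variation CV. The overstatement then shifts the z-score by ln(1 + overstatement)/CV, and the share above a cut-off is 1 − Φ(cut-off − shift). Further assumptions, none from the documents: 130 cm, 6 cm/year, CV 0.12 to 0.20, every child's height equally old, and two sets of true shares at or above the 85th and 95th percentiles.

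Example, with a 6-month-old height, CV 0.15 and a true share of 15% at or above the 85th percentile: (130/127)² = 1.048; ln 1.048 / 0.15 = 0.31; 1 − Φ(1.036 − 0.31) = 23%.

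| True share | 3 months | 6 months | 12 months |
|---|---|---|---|
| ≥85th: 15% | 18–20% | 21–26% | 29–40% |
| ≥95th: 5% | 6–7% | 8–11% | 12–20% |
| ≥85th: 35% | 39–42% | 44–50% | 54–66% |
| ≥95th: 20% | 23–26% | 27–33% | 36–48% |

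With a same-day height every row stays at its true share.

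**Step 3: when the error can arise.** Because BMI is used at baseline, what matters is the age of the height at Visit 1. The age is zero if the Visit 1 height is used. It is above zero if, for example, Visit 1 was remote, or the study height was not entered in EPIC and the download returned an older value. The documents give neither the frequency of these cases nor the age of EPIC heights.

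**The case against.** The case for the plan is substantial.

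- **The SAP sees the problem and names a remedy.** It warns of the bias and raises outcome-blind interpolation directly afterwards. This stands, but naming an option is not adopting it: an analyst could carry every missing height forward and comply fully.
- **EPIC is a permitted source.** A reader might infer that the protocol guarantees a measured height at each visit, so that carrying forward is never needed. The documents do not support that. The schedule sets the intention, while chart abstraction, phone follow-up of controls and remote visits mean some measured heights will not exist. A rule for missing heights is needed; the question is which one.
- **Baseline use limits the damage.** Visit 1 includes height for everyone, and the SAP's own caution is about bias that builds up over time. If Visit 1 heights reach EPIC, the download may already return them. This stands, and it makes the error conditional.
- **Difference between arms.** A reader might infer that the error differs between arms, because primary care children attend the office while controls may be phoned. That would need a planned analysis of follow-up BMI, and there is none: BMI is not among the outcomes in SAP Table 5.1.1. At baseline the same measurements are scheduled in both arms, and a height carried into baseline was recorded before child-level allocation.
- **BMI has a small role.** It enters the weights only if it fails the balance check, and it is not in the SAP's list of child-level subgroup factors (Table 6.1b). Its moderator role rests on Protocol 6.3.3 alone.

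**Conclusion.** The point holds as a minor defect of specification. The SAP requires a rule that it recognises as prone to bias, sets no limit on the age of the height, and does not rank sources, although the trial schedules a better measurement at Visit 1. Where the height used is stale, BMI is overstated: about 2.4% at 3 months, 4.9% at 6 months and 10% at 12 months under the assumed 128 cm and 6 cm/year. The category shifts in the working depend on further assumptions about the BMI distribution and on all heights being equally old, so they show what could happen and are not estimates for this trial.

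Two stronger conclusions should be avoided. One is that children are in fact being placed in higher BMI categories; without the age of EPIC heights this remains only a possibility. The other is that the primary result is biased; error in one baseline covariate adds noise and an upward shift to that covariate, but it does not directly bias the randomised comparison of ACQ scores.

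**What to change.** Replace the carry-forward sentence in SAP 5.1.2 with a rule along these lines:

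1. Baseline BMI uses the Visit 1 height and weight taken on the same date.
2. If no same-date height exists, height is interpolated between the nearest measured heights on either side. If there is a measurement on one side only, height is extrapolated along the child's height-for-age z-score.
3. Both steps are done without regard to outcome or arm, and height is not carried forward.
4. The same rule applies to any BMI computed at follow-up.

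Reporting how many baseline values came from each source would show whether the issue mattered. The SAP is dated as finalised on 13 September 2022, so the change belongs in a dated amendment.

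The cost is SAP wording and a little extra programming for remote visits and missing heights. No new data collection is needed, because the rule uses heights already scheduled or held in the record.

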5.1.3 Patient-level analysis – marginal models

Second, marginal models using generalized estimating equations (Fitzmaurice 2011) will produce robust estimates that adjust for clustering at the school level. These methods tend to be robust for

non-continuous outcomes (non-identify link models) and those outcomes will likely apply to our outcomes of asthma control (possibly a log gamma model) and number of symptom days (possibly a log link Poisson or negative binomial model). In contrast to mixed effects models, marginal models do not rely on numerical integration. In addition to generalized estimating equations, quasi-least squares regression (Shults and Hilbe, 2014) will also be implemented. Quasi-least squares regression is an approach for estimation of the correlation parameters that is in the framework of generalized estimating equations; it allows for application of correlation structures that were previously unavailable for generalized estimating equations and can sometimes be implemented when generalized estimating equations fails to converge.

Marginal models tend to work poorly for designs with small numbers of clusters. In our case, the number of clusters (36) is relatively large. Nevertheless, we shall implement at least one method for adjusting for a number of clusters that is not large, as implemented in Stata's program xtgeebcv program (Gallis 2019) and R's program "saws" (Fay and Graubard 2001).

5.1.4 School-level analysis -- randomization-test-based methods.

Third, assumption-free, randomization-test-based (permutation test) methods that do not rely on assumptions of parametric models will also be applied. (Berger, 2000; Good, 2005; Small, 2008; Tang 2009; Rosenbaum 2002). (Also see Hayes and Moulton 2017)

We will use conventional levels of statistical significance (p=0.05) for all pre-specified comparisons for these aims. We shall not apply Bonferroni corrections for estimates from different modeling methods that use the same specification.

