5.3 Missing data

Missing data on covariates will be handled using formal multiple imputation as needed (Little 2002; 1992; Molenberghs 2007). The proposed mixed effects models make limited assumptions of "missing at random" (MAR). To the extent that children are lost to follow-up, we shall include in our models covariates that are associated with the probability of dropout, to limit confounding by dropout. We anticipate no school withdrawals. The primary analysis will be "as randomized" (also called intention to treat). Reporting will follow the CONSORT guidelines for randomized studies and cluster randomized designs. (Altman 2012; Elbourne and Campbell 2001).

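### Adjustment covariates are chosen by an undefined imbalance check and used only through propensity weights, so balanced prognostic covariates add no precision and the adjustment set is not fixed in advance

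*SAP*

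**What the plan says.** The covariate plan is in SAP 5.1.2, Measuring outcomes over time, and has three steps.

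1. Balance check: "we shall first examine balance across the 4 treatment groups in child-level characteristics". The tools are percentages, standardized differences, distributions and graphs. No cut-off is stated.
2. Selection and weighting: "Covariates that do not demonstrate balance will be included in an initial multinomial logit model (with the 4 treatments as outcomes". After that, "using generalized propensity scores, we will develop inverse probability of treatment assignment weights".
3. Response model: "The response model will be a weighted longitudinal model using splines for time and time by treatment interaction terms". No baseline covariates are listed for it.

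The same section says that "imbalances in child characteristics are possible at the school level but are not likely at the treatment assignment level", meaning the four cells. Its covariate table already lists age group, prior-year oral steroid courses, ED visits and inpatient visits.

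Two other routes bring in baseline information. ACQ at month 0 is one of the repeated outcome measurements. For dropout, SAP 5.3 says "we shall include in our models covariates that are associated with the probability of dropout".

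No variance method is stated for the weighted model. SAP 5.1.3 says of the marginal models that they "will produce robust estimates that adjust for clustering at the school level", with a small-sample correction, and SAP 6.1.3 uses a school-level bootstrap for subgroup intervals. Neither says whether the weights are taken as known or re-estimated, and the SAP does not say which of its three analysis approaches use them.

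**The concern.** In a randomised comparison, a baseline covariate earns its place in the model because it predicts the outcome. Observed imbalance is a poor guide to that. A strong predictor that happens to be balanced still reduces residual variance when it is in the outcome model, while a weak predictor that happens to be unbalanced contributes little. The SAP's rule admits the second and drops the first.

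Because no threshold is set, the rule does not define one analysis. The adjustment set could run from nearly every candidate to none, and the choice stays open after the SAP's finalisation date. The rule looks at baseline data and not at outcomes, so it is not outcome-driven selection in itself. It does leave the primary model unspecified.

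What is at stake is precision, mainly for the simple cell contrasts of Aims 1b and 1c (Protocol 2.1). SAP section 8 gives these as little as 0.75 (a vs b) and 0.71 (c vs d) power at n=432.

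**Working it through.** **Inputs from SAP section 8:** 36 schools of 12 children, so n=432, 216 per arm for a main effect and 108 per cell; effects of 0.35 SD (child level) and 0.5 SD (school level), no interaction; ICC 0.06; design effect 1+0.06×11=1.66. Alpha is 0.05, taken as two-sided.

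**Step 1. Reproduce the plan's figures.** With SD 1, power = Φ(d/SE − 1.96) and SE = √(2·DEFF/n per group).

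- A main effect: SE = √(2/216) = 0.0962; 0.35/0.0962 = 3.64; power 0.953 (stated 0.95).
- S main effect: SE = √(2×1.66/216) = 0.124; 0.5/0.124 = 4.03; power 0.981 (stated 0.97).
- a vs b: SE = √(2/108) = 0.136; 0.35/0.136 = 2.57; power 0.73 (stated 0.75).

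**Step 2. Prespecified adjustment, closed form.** Covariates explaining a share R² of the variance multiply the SE by √(1−R²). R² is not in the documents, so a range is shown.

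| R² | SE factor | a vs b | A main effect |
|---|---|---|---|
| 0 | 1.00 | 0.73 | 0.95 |
| 0.1 | 0.95 | 0.77 | 0.97 |
| 0.2 | 0.89 | 0.82 | 0.98 |
| 0.3 | 0.84 | 0.87 | 0.99 |

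**Step 3. Simulate the SAP's rule.** 36×12 children, school SD 0.25, a change-score outcome and 1,500 runs per setting. Assumed: eight covariates with joint R² of 0.1 to 0.3 and covariate ICC 0.05. A covariate counted as unbalanced if its largest pairwise standardized difference across the four cells exceeded the threshold. The weighted analysis used cluster-robust SEs with the weights treated as known.

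| Threshold | Mean covariates kept (of 8) | Reported SE / true SD, A main effect, R² 0.1, 0.2, 0.3 |
|---|---|---|
| 0.10 | 7.2 | 1.02, 1.09, 1.18 |
| 0.25 | 2.5 | 1.02, 1.03, 1.07 |
| 0.40 | 0.3 | 1.00, 0.99, 1.04 |

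Across all contrasts the ratio ran from 0.97 to 1.18. With a school-level bootstrap that refits the weights (R² 0.2, 300 runs, about 4% Monte Carlo error), it was 0.97 (A) and 1.03 (S) at threshold 0.25, and 0.95 and 0.89 at 0.10. That shows no systematic overstatement.

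True SD of the A main-effect estimate at R² 0.2:

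| Threshold | Unadjusted | Weighted | Regression |
|---|---|---|---|
| 0.10 | 0.094 | 0.089 | 0.086 |
| 0.25 | 0.098 | 0.093 | 0.089 |
| 0.40 | 0.096 | 0.096 | 0.087 |

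Weighting recovers (0.094−0.089)/(0.094−0.086), about 0.6 of the gain, at 0.10; (0.098−0.093)/(0.098−0.089), also about 0.6, at 0.25; and essentially none at 0.40.

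**Step 4. Power for a vs b.** Simulated power was 0.72 to 0.75 with weights treated as known, 0.73 to 0.76 unadjusted, and 0.77 to 0.88 with prespecified regression. The regression figures are slightly flattered, because their cluster-robust SEs had no small-sample correction and ran a few percent low. The closed form (0.77 to 0.87) does not depend on that.

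**Step 5. How much of the gap is the SE, and how much the selection?** Putting the true SDs at R² 0.3 into Φ(0.35/SD − 1.96):

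| Threshold | Weighted SD → power | Regression SD → power |
|---|---|---|
| 0.10 | 0.1153 → 0.86 | 0.1112 → 0.88 |
| 0.25 | 0.1293 → 0.77 | 0.1164 → 0.85 |
| 0.40 | 0.1305 → 0.77 | 0.1127 → 0.87 |

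With a correct SE and a low threshold, weighting comes close to regression. At 0.25 and above the loss remains whatever variance method is used, because the covariates were not selected.

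**The case against.** Several points on the other side stand.

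- **Standard errors.** A reader might infer that the plan will report SEs that are too large. The documents do not support this as fact, since no variance estimator is named for the weighted model. Overstatement appears only if the weights are treated as known and enough prognostic covariates enter. Where it occurs it is conservative and does not inflate type I error.
- **Source of imbalance.** A reader might also say that assignment is random, so all imbalance is chance. SAP 5.1.2 gives dropout as a reason for checking, SAP 5.4 moves children between cells, and children are not themselves randomised to schools (Protocol 3.1). This does not rescue the rule. A treatment-assignment model is not a dropout model, SAP 5.3 handles dropout separately, and regression on the same covariates would also address such imbalance.
- **Contradiction between sections.** The mixed-model and marginal-model sections do not mention weights, but they do not say unweighted either. That is silence, and calls for clarification.
- **School-level balance.** The weights were never meant to repair it. Constrained and paired randomisation (SAP 3.1) was.
- **Extent of the loss.** Baseline ACQ and dropout predictors keep some prognostic information in the models, and weighting recovers part of the gain for covariates that are selected. Main effects lose little: at R² 0.1 to 0.2 the A main effect would rise only from 0.95 to 0.97 or 0.98.

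**Conclusion.** The concern holds as a matter of precision and prespecification. The SAP chooses covariates by observed imbalance with no threshold, and apart from the dropout provision uses them only through weights. The analysis could adjust for almost all the listed covariates or almost none.

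For a simple contrast such as a vs b at n=432, the cost is the difference between about 0.72 to 0.75 and about 0.77 to 0.88 power. This rests on R² of 0.1 to 0.3, eight covariates, the thresholds shown, a single change score in place of the spline model, and, for the weighted figure, weights treated as known. If the threshold were low and the variance re-estimated the weights, most of the gap would close. For main effects the difference is a few points.

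No bias or type I error inflation is shown. SEs that are too large by up to 18% are a possibility under one variance method, not something the plan commits to.

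**What to change.** **Primary analysis.** Replace the balance trigger and the weights with a fixed covariate set in the outcome model, the same for the mixed and marginal models:

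- child level: age group, prior-year oral steroid courses, ED visits and inpatient visits;
- school level: a small number of randomisation factors available for every school, for example charter status or randomisation wave, enrolment and attendance. Facility index should not be required, because SAP 3.1 reports facility-condition data as lacking for the charter wave.

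Keep the balance tables and plots as description only.

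**If weights are kept as a sensitivity analysis**, state:

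- the balance threshold;
- which analysis approaches use the weights;
- how children in cells e and f are handled, since the weight model has four categories but the marginal navigator contrast in SAP section 2 is a+c+e against b+d+f;
- a variance method that re-estimates the weights, such as a school-level bootstrap that refits them in each resample.

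**Cost.** SAP wording, no new data collection, and a few school-level degrees of freedom for the S contrast. With about 36 schools the school-level list should stay short.
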